# 4. Trial Design

# 4.1. Overall Design

The trial consists of 2 parts: Part 1 (dose titration) and Part 2 (dose expansion). Part 2 consists of four arms: Arms 1A and 1B (mCRPC patients) and Arms 2 and 3 (LPC patients).

Part 1 contains a dose titration for initial safety assessment and identification of the recommended expansion dose range (REDR). It will enroll mCRPC patients to receive BNT112 monotherapy at 3 predefined dose levels (DLs) until a discontinuation-of-treatment criterion is met (Section 7). Part 1 of the trial will employ a modified 3+3+3 design (adapted from Hamberg et al. 2010^13) with up to 9 evaluable patients.

Once the REDR is defined, the trial will commence with Part 2 and enroll approximately 106 patients in four arms (the expansion part, Section 4.2). Part 2 Arms 1A and 1B will enroll patients with mCRPC to receive BNT112 monotherapy or BNT112 in combination with cemiplimab, and Part 2 Arms 2 and 3 will enroll patients with newly diagnosed LPC eligible for treatment with ADT (e.g., goserelin acetate) to receive BNT112 monotherapy or BNT112 in combination with cemiplimab.

Enrollment between Arms 1A and 1B in Part 2 and between Arms 2 and 3 will be randomized 1:1 to avoid enrollment bias.

The treatment in Part 2 Arms 1A and 1B will continue until a discontinuation-of-treatment criterion is met (Section 7). In Part 2 Arms 2 and 3 the treatment will be stopped at Cycle 8 Day 1 (C8D1) or until a discontinuation-of-treatment criterion is met (Section 7).

The safety of BNT112 in doses  $\mu$ g,  $\mu$ g, and  $\mu$ g, and  $\mu$ g will be evaluated based on DLTs during the first treatment cycle (21 days) as well as the overall incidence of BNT112-related or potentially related TEAEs in both parts of the trial. The safety of concomitant administration of cemiplimab will be evaluated based on the overall incidence of cemiplimab-related or potentially related TEAEs in Part 2 Arms 1A and 2 of the trial and will follow the same rules as Part 1, until the SRC reviews and confirms that the combination safety profile is acceptable to continue with the enrollment for the combination arms. The safety will be evaluated by the SRC. For details, please refer to Section 9.6 and the SRC charter.

The efficacy measurement in mCRPC patients (i.e., Part 1 and Part 2 Arms 1A and 1B) will be tumor response assessment by on-treatment imaging every 8 weeks (±7 days) for 24 weeks, and then every 3 months (±7 days) thereafter until a discontinuation-of-treatment criterion is met (Section 7) as assessed by the investigator. The Prostate Cancer Working Group 3 (PCWG3) criteria and immune-modified Response Evaluation Criteria in Solid Tumors (iRECIST) criteria will be used for endpoint response evaluation. If the investigator considers radiographic changes secondary to drug-induced inflammation and not to tumor progression, the investigator may postpone a diagnosis of PD until the next radiographic evaluation in the trial.

Following progression after BNT112 monotherapy, patients in Arm 1B will have the option to be treated with cemiplimab monotherapy.

The efficacy in LPC patients (i.e., Part 2 Arms 2 and 3) will be assessed by tumor measurement using mpMRI or MRI consistently throughout the trial. The same imaging modality should be used at screening and at all subsequent assessments.

CONFIDENTIAL Page 46 of 122

Various blood- and tumor-based biomarkers will be analyzed in both parts.

The trial will be conducted in approximately 30 trial centers in up to 5 countries.

Trial periods are provided in the Schedule of Activities (SoA).

#### 4.1.1. Part 1

Trial Part 1 will identify the REDR of BNT112 monotherapy in patients with histologically confirmed mCRPC who progressed after at least 2 but no more than 3 lines of life-prolonging systemic therapy (e.g., abiraterone or enzalutamide, docetaxel, cabazitaxel) or who cannot tolerate or have refused any of these therapies.

Three doses of BNT112 cancer vaccine will be used for an intra-patient dose titration accommodating the inter- as well as intra-patient variability of the immune system activation:

- DL1 [starting dose]: μg of total RNA μg of RNA of each antigen)
- DL2 [intermediate dose]: DL2 [intermediate d
- DL3 [target dose]: CC μg of total RNA (CC μg of RNA of each antigen)

One additional DL of CCI µg of total RNA (with GCI µg of RNA of each antigen) can be used for dose reductions (see Section 6.6.1).

BNT112 will be given in the following dose schedule: D1, D8, and D15 of C1 and C2 and D1 from C3 onwards. The individual dose titration will be conducted during C1 with DL1 on D1, DL2 on D8 and DL3 on D15.

For the first 3 patients: (i) patients will be enrolled in a staggered manner with a safety monitoring interval of at least 1 week between the first and the second patient, and between the second and the third patient, and (ii) an overnight stay is required on C1D1, C1D8, and C1D15. On the 17 MAY 2021, the SRC recommended that patient monitoring can be limited to 4 to 6 h and no overnight stay is required.

A minimum of 3 patients will be evaluated for a DLT assessment period defined as 1 cycle (21 days), see Section 6.6.1.1. At the discretion of the investigator, the dose of BNT112 may be maintained at the current DL for 1 dose, i.e., intra-patient dose titration may be delayed (see Section 6.6.1.1). For these patients, the DLT assessment period is extended to 28 days.

The dose titration will be conducted according to the following rules (also refer to Table 4-1):

- If none of the first 3 DLT evaluable patients in Part 1 experience a DLT at any given DL (i.e., [60] µg, and [60] µg), the REDR will be confirmed and Part 2 will be initiated.
- If 1 of the first 3 DLT evaluable patients in the Part 1 experiences a DLT, 3 additional patients will be enrolled in Part 1.
- If fewer than 2 of 6 DLT evaluable patients in Part 1 experience a DLT/DLTs (i.e., no additional DLTs in the last 3 patients), Part 2 will be initiated.
- If 2 of the first 6 DLT evaluable patients in Part 1 experience a DLT, the cohort will be expanded to 9 patients.

CONFIDENTIAL Page 47 of 122

- If 2 of the 9 DLT evaluable patients in Part 1 experience a DLT (no additional DLTs in the last 3 patients), Part 2 will be initiated.
- If 3 or more of up to 9 DLT evaluable patients in Part 1 experience DLTs, accrual will be halted. In this case, the REDR will have been exceeded and dose titration will stop. However, an intermediate DL below the REDR may be explored. If the REDR is exceeded, the highest dose at which fewer than 3 DLT evaluable patients experience a DLT will be declared the REDR.

In addition, if 2 or more patients in the first 3 patients cannot dose escalate to the target dose by C1D21 in the absence of a DLT, the cohort will be expanded to 6 patients (this situation will be regarded equivalent to an occurrence of 1 patient with DLT).

Each patient may experience a maximum of 2 dose titration steps. The highest tolerated dose given during dose titration should then become the standard dose for that patient to be given for the remainder of the trial unless dose reduction is required.

All patients will be closely monitored for TEAEs during the DLT assessment window. TEAEs identified as DLTs will be reported to the sponsor within 24 h. Any patient in Part 1 who does not complete the DLT assessment window for a reason other than a DLT will be considered non-evaluable for the REDR assessment and may be replaced by an additional patient. Any patient who received < 3 doses of BNT112 during the first cycle for a reason other than a DLT will be considered non-evaluable for the REDR assessment and may be replaced by an additional patient.

**Table 4-1: Dose Titration Scenarios and Rules** 

Dose (μg)	0 DLT scenario	1 DLT	2 DLT scenarios						3 or more DLT scenarios					
CCI	0	0	0	1	0	0	2	0	1	1				
	0	0	1	0	0	2	0	1	0	1				
	0	1	0	0	2	0	0	1	1	0	> 2 DLTs across			
Total number of patients required	3	(	9						any DLs					
Action	Move to expansion	If expans DLT at If 2/9	If 2/9	If 2/9 move to expansion; if >2/9 then hold and go to SRC.				then	Hold and go to SRC.					

Abbreviations: DLT = dose-limiting toxicity; SRC = Safety Review Committee.

After DLT assessment has been completed in Part 1, safety data will be reviewed by the SRC to determine the REDR. The SRC may recommend, on the basis of emerging clinical safety, and

CONFIDENTIAL Page 48 of 122

pharmacodynamics data from this trial, that other DLs and dosing schedule of BNT112 may be evaluated in the trial.

#### 4.1.2. Part 2

Part 2 will further explore the safety and pharmacodynamics of BNT112 at the REDR in patients with mCRPC (Arms 1A and 1B) and LPC (Arms 2 and 3) and to evaluate the preliminary clinical response. In all arms, BNT112 will be given in the following dose schedule: D1, D8, and D15 of C1 and C2 and D1 from C3 onwards. The individual dose titration will be conducted during C1 with DL1 on D1, DL2 on D8 and DL3 on D15. The highest tolerated dose given during dose titration should be administered for the remainder of the trial unless dose reduction is required. The treatment will continue until a discontinuation-of-treatment criterion is met (Section 7). In Part 2 Arms 2 and 3 the treatment will be stopped at C8D1.

Initially, patients will be monitored in the hospital overnight post-treatment at all visits in C1. On the 17 MAY 2021, the SRC recommended that patient monitoring can be limited to 4 to 6 h and no overnight stay is required.

#### Part 2 Arms 1A and 1B (mCRPC)

Approximately 66 (33 per arm) patients with histologically confirmed mCRPC, who progressed after at least 2 but no more than 3 lines of life-prolonging systemic therapy (e.g., abiraterone or enzalutamide, docetaxel, cabazitaxel) or who cannot tolerate or have refused any of these therapies will be enrolled in Part 2 Arms 1A and 1B. Enrollment between Arms 1A and 1B will be randomized 1:1 to avoid enrollment bias.

Following progression after BNT112 monotherapy, patients in Arm 1B will have the option to be treated with cemiplimab monotherapy.

## Part 2 Arm 2 and Arm 3 (LPC)

Treatment-naïve patients with LPC (i.e., N0, M0), defined according to European Association of Urology Guidelines on Prostate Cancer (2018) and in line with the U.S. National Comprehensive Cancer Network (NCCN 2020), who are eligible for treatment with ADT (e.g., goserelin acetate) followed by radical prostatectomy will be enrolled in Part 2 Arms 2 and 3. Enrollment between Arms 2 and 3 will be randomized 1:1 to avoid enrollment bias.

#### 4.2. Planned Number of Patients

There will be 3 to 9 patients in Part 1 (dose titration part, single arm) and up to 106 patients in Part 2 (expansion part, four arms: up to 33 patients in Arm 1A and Arm 1B, respectively, and approximately 20 patients in Arm 2 and Arm 3, respectively). Drop-outs may be replaced. In total, there will be approximately 115 patients.

Re-screening of patients is allowed.

# 4.3. Trial Design Rationale

This trial is designed to evaluate the safety, tolerability, immunogenicity, and preliminary efficacy of BNT112 in monotherapy and in combination with cemiplimab in mCRPC and LPC patients eligible for treatment with ADT (e.g., goserelin acetate) followed by radical prostatectomy.

CONFIDENTIAL Page 49 of 122

In Part 1, a modified 3+3+3 design (adapted from Hamberg et al. 2010^13) will be applied with approximately 3 to 9 patients enrolled. This modified 3+3+3 design is used to reduce the chance of incorrectly ceasing enrollment at a certain step-up DL, when inter- and intra-patient variability is expected and the true DLT rate may be <5%. If > 1 patient of the first 3 patients or > 2 patients of the first 6 patients experiences a DLT, no additional patients will be enrolled at that DL, in order to avoid patients being treated at DLs with unacceptable toxicities. Furthermore, intrapatient dose titration is implemented and is justified in detail in the next section.

Patients eligible for Part 1 and Part 2 Arms 1A and 1B of this trial will have histologically confirmed mCRPC and have progressed after at least 2 but no more than 3 lines of life-prolonging systemic therapy (e.g., abiraterone or enzalutamide, docetaxel, cabazitaxel) or cannot tolerate or have refused any of these therapies. These lines of therapy include life-prolonging therapies administered in the metastatic hormone–sensitive setting. This description defines a population in which it is ethically acceptable and feasible to evaluate the safety, tolerability, immune response, and pharmacokinetics of novel therapies intended for the treatment of patients with advanced malignancies.

Immune therapies based on antigen-specific T cells have the highest probability of success in patients with low tumor burden and at an early stage of the tumor's life cycle. Therefore, patients eligible for Part 2 Arms 2 and 3 of this trial will have a newly diagnosed LPC and will be candidates for neoadjuvant treatment with LHRH agonist or antagonist followed by radical prostatectomy. LPC patients will be enrolled only after the initial safety assessment in the dose titration part of Part 1 is completed and the REDR is defined (for further details please also refer to Section 2.2).

Both clinical trial populations were selected and refined together with clinical experts from the field to enable the real-life clinical setting where the benefit for the patients might be the highest. The clinical setting is further justified by several factors recognized as relevant and important for development of cancer vaccines, also listed in the FDA Guidance for Industry "Clinical Considerations for Therapeutic Cancer Vaccines". These include the time to develop an anti-tumor response, which is generally longer for immunotherapies, and the higher chance for a cancer vaccine to show efficacy in lower tumor burden patients and patients with limited prior therapy exposure.

All patients in Part 2 Arms 2 and 3 will receive up to 3 DLs of BNT112 during the C1 intrapatient dose titration based on the REDR defined in Part 1, thereby allowing for a safe combination with cemiplimab. The safety of this combination is further supported by data from the ongoing Lipo-MERIT trial where no differences were seen between RNA-LPX monotherapy and combination with anti-PD-1 or BRAF/MEK (serine/threonine-protein kinase B-Raf/mitogen-activated protein kinase kinase) inhibitors. All combinations in that trial indicate a well-tolerated safety profile of these combinations with Lipo-MERIT vaccine doses ranging from Lipug to Lipug. Safety of the treatment arms with BNT112 and cemiplimab combination will be reviewed and will follow the same rules as Part 1, until the SRC reviews and confirms that the combination safety profile is acceptable. Based on the recommendation from the SRC, the sponsor will decide if enrollment should continue for the combination arms. More details are provided in the SRC charter.

Randomization in a 1:1 ratio between Part 2 Arms 1A and 1B and between Part 2 Arms 2 and 3 is included to avoid enrollment bias.

CONFIDENTIAL Page 50 of 122

Eligibility criteria are based primarily on clinical safety data from the Lipo-MERIT trial as well as standard eligibility criteria for mCRPC and LPC.  Eligibility criteria for the Part 2 Arm 2 (combination with cemiplimab) of the trial are, in addition, based on available safety data for cemiplimab as well as studies with anti-CTLA-4 and with anti-PD-1 treatments. 

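### For 2 DLTs in the first 3 patients, Protocol 4.3 stops enrolment at that dose level while Table 4-1 continues to 9, and the Part 1 rules are carried to the combination arms

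*Protocol*

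**What the plan says.** Protocol 4.3 (Trial Design Rationale) gives a stopping trigger, "If > 1 patient of the first 3 patients or > 2 patients of the first 6 patients experiences a DLT", and its consequence: "no additional patients will be enrolled at that DL". The stated purpose is to keep patients away from dose levels with unacceptable toxicity.

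Protocol 4.1.1 lists the Part 1 rules as bullets. No DLT in the first three evaluable patients confirms the dose range. The bullet that begins "If 1 of the first 3 DLT evaluable patients in the Part 1 experiences a DLT" adds three patients. A later bullet says "If 2 of the first 6 DLT evaluable patients in Part 1 experience a DLT, the cohort will be expanded to 9 patients". The halting bullet says "If 3 or more of up to 9 DLT evaluable patients in Part 1 experience DLTs, accrual will be halted". No bullet names two DLTs in the first three patients.

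Table 4-1, to which 4.1.1 refers, has six two-DLT columns: three with both DLTs at one dose level and three with the DLTs at different levels. They share a requirement of nine patients and one action: "If 2/9 move to expansion; if >2/9 then hold and go to SRC".

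Section 4.1 places the safety review of concomitant cemiplimab in "Part 2 Arms 1A and 2 of the trial and will follow the same rules as Part 1". Section 4.3 and the Methodology part of the synopsis also carry the Part 1 rules over to the combination.

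**The concern.** With exactly two DLTs in the first three evaluable patients, someone following 4.3 closes the dose level, and someone following Table 4-1 keeps enrolling towards nine. A threshold that protects patients should lead to one action wherever it is looked up.

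Part 1 is finished, so the carry-over is what keeps the point open: the combination review "will follow the same rules as Part 1, until the SRC reviews and confirms that the combination safety profile is acceptable". Neither document says that this confirmation has been given. The SRC review of 17 May 2021 is described as covering patients in Part 1. The SAP does not settle the rule either, because it defines its DLT evaluation set for Part 1 only.

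**Working it through.** **Inputs.** Protocol 4.3: stop at 2 or more of the first 3, or 3 or more of the first 6. Protocol 4.1.1 with Table 4-1: two DLTs continue towards 9, and accrual halts at 3 or more. Cohorts of three are counted as whole cohorts, and patients are independent with a common DLT rate p. The only rate that the protocol mentions is below 5%, in 4.3; the rates from 10% to 50% are assumptions.

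**The plan's own figure.** Protocol 9.2 gives 3 to 9 evaluable patients for Part 1. Both readings can end at 3, 6 or 9 patients, so this range is reproduced but does not show which rule is meant.

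**Where the readings part.**

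| DLTs | 4.3 | 4.1.1 | Table 4-1 |
|---|---|---|---|
| 2 of first 3 | stop at that level | not named; halt only at 3 or more | go to 9; hold if more than 2 |
| 3 of first 3 | stop | halt | hold |
| 3 or more of first 6 | stop | halt | hold |

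Only the first row differs.

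**Probability of the disputed state.** P(exactly 2 of 3) = 3p²(1−p). At p = 0.20 this is 3 × 0.04 × 0.80 = 0.096.

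**What follows from that state.** Under 4.3, nobody further is treated at that level and the chance of expansion is 0. Under Table 4-1, three more patients are treated. If none has a DLT, another three follow, and expansion needs 0 DLTs in all six, with probability (1−p)⁶. At p = 0.20 this is 0.262.

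**Overall chance of expansion.**
- Under 4.3: (1−p)³ + 3p(1−p)²·(1−p)³ + [3p(1−p)²]²·(1−p)³. At p = 0.20: 0.512 + 0.384 × 0.512 + 0.384² × 0.512 = 0.7841.
- Under Table 4-1: the same plus 3p²(1−p)·(1−p)⁶. At p = 0.20: 0.7841 + 0.096 × 0.2621 = 0.8093.

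| p | P(2 of 3) | (1−p)⁶ | Expansion, 4.3 | Expansion, Table 4-1 | Difference (points) | Expected N, 4.3 / Table 4-1 |
|---|---|---|---|---|---|---|
| 5% | 0.7% | 73.5% | 98.92% | 99.44% | 0.52 | 3.46 / 3.50 |
| 10% | 2.7% | 53.1% | 94.92% | 96.35% | 1.43 | 3.91 / 4.05 |
| 20% | 9.6% | 26.2% | 78.41% | 80.93% | 2.52 | 4.59 / 5.03 |
| 33% | 21.9% | 9.0% | 49.38% | 51.36% | 1.98 | 4.93 / 5.78 |
| 50% | 37.5% | 1.6% | 18.95% | 19.53% | 0.59 | 4.55 / 5.81 |

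Differences are taken before rounding.

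**Counting unit.** The enumeration counts any two DLTs in three patients. Section 4.3 speaks of a single dose level, so two DLTs at different levels may not trigger it. The probabilities and differences above are therefore upper bounds if 4.3 is read as two DLTs at one level.

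**The case against.** The best defence is that 4.1.1 can be read together with 4.3. Its bullets run in sequence. Three more patients are added only after one DLT in the first three. The bullet on fewer than 2 of 6 explains itself as no further DLT in the second three, which presupposes entry with one. The rule for patients who cannot reach the target dose is likewise equated with one DLT. On that reading, 2 of the first 6 means one in each cohort, and 4.3 supplies the 2-of-3 action that 4.1.1 leaves open. A reader might infer that 4.1.1 itself orders expansion to nine after 2 of 3. The text does not say so, and to that extent the defence stands.

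It does not remove the conflict. The halting bullet and the legible two-DLT action in Table 4-1 set no condition on when the DLTs occur, and three of the table's columns put both at one level, where the wording of 4.3 bites directly. The table's one-DLT action cell is garbled in the text examined, so a condition placed there cannot be wholly excluded.

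Three further points limit the weight:
- At 5% the disputed state is rare, and Protocol 2.3 reports no DLTs during dose escalation in earlier trials of the vaccine class.
- Section 4.1 bases combination safety on the overall incidence of related events, the DLT criteria section is titled for Part 1, and detail is left to an SRC charter that is not among the documents. Whether the carry-over means these exact counts is itself unclear.
- Arm 1A is closed, and the SRC may already have confirmed the combination.

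A reader might also infer, from nine patients dosed in Part 1, that the two-DLT path was taken against 4.3. The documents do not support this: they give no DLT count for Part 1, and they allow non-evaluable patients to be replaced.

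**Conclusion.** The inconsistency is real and lies mainly between 4.3 and Table 4-1. Section 4.1.1 is silent on 2 of 3, but its halting rule sides with the table. The counting units differ as well.

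The size is mixed. The chance of reaching the state is 0.7% at 5%, and 9.6% and 21.9% at assumed rates of 20% and 33%. A reader might infer that the design's overall behaviour is at stake, but the chance of moving to expansion shifts by at most about 2.5 points at the rates tested. The consequence lies in the state itself, where one reading treats nobody further at that level and the other treats three to six more patients.

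The remaining reach is narrow. Part 1 is complete. SAP 8.7.6 records that enrolment to Arms 1A and 1B stopped after the August 2022 interim analysis, and SAP 5 says this was before the planned LPC enrolment was complete. That leaves Arm 2, and only until the SRC confirms the combination profile. If confirmation has been given, what is left is a correct record of the rule.

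The figures assume independent patients, a common DLT rate and whole cohorts of three.

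**What to change.** Reconcile Protocol 4.1.1, Table 4-1 and 4.3 so that they state the same action for two DLTs in the first three evaluable patients, and the same counting unit (per dose level or across levels). Point the carry-over statements in the synopsis Methodology, 4.1 and 4.3 to that text, and bring the SRC charter into line. Which action is right is for the sponsor and SRC to decide.

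The cost is wording: a protocol amendment or clarification letter, plus a charter update. No new data or analysis is needed.
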